# Table 3.4.3-1 Exclusion Criteria Rollover Subjects from Trial 331-201-00080 or 331-201-00081 30. Subjects with a major protocol violation during the course of their participation in the double-blind phase 3 trial (ie, Trial 331-201-00080 or 331-201-00081). Minor violations such as occasional visits outside of the acceptable window or a missing blood draw will not exclude a subject from participation in Trial 331-201-00083; however, continual lack of compliance with the visit schedule, trial assessments, or treatment regimen in the prior double-blind trial would be considered a major violation that would result in exclusion from Trial 331-201-00083. The medical monitor should be contacted if the investigator is unsure of a subject's eligibility.

AE = adverse event; ALT = alanine aminotransferase; AST = aspartate aminotransferase; BMI = body mass index; CPK = creatine phosphokinase; C-SSRS = Columbia-Suicide Severity Rating Scale; DBP = diastolic blood pressure; ECG = electrocardiogram; HbA1c = glycosylated hemoglobin; HIV = human immunodeficiency virus; IDDM = insulin dependent diabetes mellitus; OTC = over-the-counter; QTcF = QT interval as corrected by Fridericia's formula; SBP = systolic blood pressure; T4 = free thyroxine; ULN = upper limit of normal; WOCBP = women of childbearing potential.

Nonchildbearing potential is defined as male and female subjects who are surgically sterile (ie, male subjects who have undergone bilateral orchidectomy and female subjects who have undergone bilateral oophorectomy and/or hysterectomy) and female subjects who have been postmenopausal for at least 12 consecutive months.

Subjects must agree to restrictions to medications and lifestyle as described in Section 4.

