## 3.7.1 Schedule of Assessments

## 3.7.1.1 Screening and Baseline

## 3.7.1.1.1 Rollover Subjects

Subjects who completed Day 21 of the double-blind trial and had no major protocol deviation will be screened for eligibility at the last visit of the double-blind trial (ie, Week 3 [Day 21] visit of Trials 331-201-00080 or Trial 331-201-00081). Subjects will sign a separate ICF for participation in Trial 331-201-00083 before any procedures specific to the open-label trial are performed. The assessments from the last visit of the double-blind trial will serve as the baseline measures for Trial 331-201-00083 for the following assessments:

[CC]

physical examination, waist circumference, vital signs, ECG, clinical laboratory tests, urine drug screen, blood alcohol, and urine pregnancy test.

Additional procedures to be performed for rollover subjects at screening/baseline of the open-label trial are as follows:

- Inclusion/exclusion criteria for Trial 331-201-00083 will be reviewed to ensure the subject's eligibility.
- Trial personnel will register the visit in the interactive web response system (IWRS).
- Medical history will be updated, if necessary.
- Concomitant medications will be reviewed to assure that the subject is not receiving any prohibited medications.
- CC
- Open-label brexpiprazole (OPC-34712) will be dispensed to the subject.
- Recording of AEs will begin with the signing of the ICF for Trial 331-201-00083.

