- Urine will be collected from all subjects for urine screen(s) for drugs of abuse.
- A urine pregnancy test will be performed for all WOCBP. All positive results must be confirmed by a serum pregnancy test. Subjects with a positive serum pregnancy test result will be withdrawn from the trial.

Confidential - Proprietary Information

49

- Adverse events and concomitant medications will be recorded.
- A confirmation of data download from the wearable device will be performed.
- Open-label brexpiprazole (OPC-34712) will be dispensed to the subject.
- Adjustment of brexpiprazole (OPC-34712) dose, if needed.
- Drug accountability will be performed.
- . CCI
- Trial personnel will access the IWRS or equivalent to register the visit.

#### 3.7.1.2.4 Week 8

All subjects will attend a visit at Week 8 ( $\pm$  2 days) for the following evaluations:

- Vital sign measurements (body temperature, blood pressure, and heart rate) will be recorded. Blood pressure and heart rate are to be measured in the following order: supine and standing after the subject has been in each position at least 3 minutes.
- A urine pregnancy test will be performed for all WOCBP. All positive results must be confirmed by a serum pregnancy test. Subjects with a positive serum pregnancy test result will be withdrawn from the trial.
- Adverse events and concomitant medications will be recorded.
- CCI
- Open-label brexpiprazole (OPC-34712) will be dispensed to the subject.
- Adjustment of brexpiprazole (OPC-34712) dose, if needed.
- Drug accountability will be performed.
- CC
- Trial personnel will access the IWRS or equivalent to register the visit.

#### 3.7.1.2.5 Week 12

All subjects will attend a visit at Week 12 ( $\pm$  2 days) for the following evaluations:

Confidential - Proprietary Information

50

- Vital sign measurements (body temperature, blood pressure, and heart rate) will be recorded. Blood pressure and heart rate are to be measured in the following order: supine and standing after the subject has been in each position at least 3 minutes.
- A standard 12-lead ECG will be performed after the subject has been supine and at rest for at least 5 minutes.
- Blood samples for clinical laboratory tests (hematology, coagulation parameters, and serum chemistry, including prolactin, HbA1c, and TSH with reflex to T4 if the result for TSH is abnormal) should be drawn after a minimum 8-hour fast.
- Samples will be obtained for blood alcohol testing.

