## 3.7.1.2.7 End of Treatment - Week 26/Early Termination

The following procedures will be performed at the Week 26, or ET, visit:

- A complete physical examination (including waist circumference) will be performed.
- Vital sign measurements (body weight, body temperature, blood pressure, and heart rate) will be recorded. Blood pressure and heart rate are to be measured in the following order: supine and standing after the subject has been in each position at least 3 minutes.
- A standard 12-lead ECG will be performed after the subject has been supine and at rest for at least 5 minutes.
- Blood samples for clinical laboratory tests (hematology, coagulation parameters, and serum chemistry, including prolactin, HbA1c, and TSH with reflex to T4 if the result for TSH is abnormal) must be drawn after a minimum 8-hour fast.
- Samples will be obtained for blood alcohol testing.
- Urine will be collected from subjects for urinalysis and urine screen(s) for drugs of abuse.
- A urine pregnancy test will be performed for all WOCBP. All positive results must be confirmed by a serum pregnancy test.
- Adverse events and concomitant medications will be recorded.
- Drug accountability will be performed.

Trial personnel will access the IWRS or equivalent to register the visit.

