9.2.2 Metabolic Change

In addition to mean change from baseline, incidence of treatment emergent significant changes in fasting lipids, fasting glucose, and metabolic syndrome will be summarized by parent study treatment group for rollover subjects and overall using the following criteria.

Criteria for Treatment-Emergent Significant Change in Lipids and Glucose					
LAB PARAMETER	LAB PARAMETER BASELINE ¹ ANYTIME POST BASELINE				
LDL Direct, Fasting	Borderline 100-<160	High >=160			
(MG/DL)	Normal/Borderline < 160	High >=160			
	Normal <100	Borderline/High >=100			
	Any Value	Increased >=30			
HDL Cholesterol, Fasting	Normal >=40	Low <40			
(MG/DL)	Any Value	Decreased >=20			
Triglycerides, Fasting	Normal <150	High 200-<500			
(MG/DL)	Borderline 150-<200	High 200-<500			
	Normal/Borderline <200	High 200-<500			
	Normal <150	Borderline/High/Very High >=150			
	Any Value	Increased >=50			
Glucose Fasting, Serum	Normal <100	High >=126			
(MG/DL)	Impaired 100-<126	High >=126			
	Normal/Impaired <126	High >=126			
	Any Value	Increased >=10			

¹ BASELINE IS DEFINED AS THE LAST AVAILABLE MEASUREMENT PRIOR TO THE FIRST DOSE OF OPEN-LABEL IMP IN THE OPEN-LABEL TREATMENT PHASE

Criteria for Treatment-Emergent Metabolic Syndrome			
DESCRIPTION	ANYTIME POST BASELINE ¹		
Central Obesity	Waist Circumference >=102cm(MALE), >=88cm (FEMALE)		
Dyslipidemia	Triglycerides >= 150mg/dl		
Dyslipidemia	HDL < 40mg/dl (MALE), <50mg/dl (FEMALE)		
Supine Blood Pressure	Systolic>=130mmHg and Diastolic>=85mmHg		
Glucose Fasting, Serum	>=100mg/dl		
Metabolic Syndrome	Met 3 Or More of the Above Criteria at a Visit		

¹ BASELINE IS DEFINED AS THE LAST AVAILABLE MEASUREMENT PRIOR TO THE FIRST DOSE OF OPEN-LABEL IMP IN THE OPEN-LABEL TREATMENT PHASE

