	for women)	> 10% increase in QTc means a subject who attains		
	And > 10% Increase	a value ≥ 450 Msec for men or ≥ 470 Msec for		

Confidential - Proprietary Information

15

Categorical Change Criteria in QT/QTc Parameters			
Classification Category Criteria		Criteria	
		women, and > 10% increase during treatment period but not at baseline	
	New Onset (> 500 Msec)	New onset (> 500 msec) in QTc means a subject who attains a value > 500 msec during treatment period but not at baseline.	
	Increase 30 - 60 Msec	Increase from baseline value > 30 and ≤ 60 msec in OTc	
	Increase > 60 Msec Increase from baseline value > 60 msec in QTc		

^{*} QTc categorical change criteria apply to QTcB, QTcF and QTcN.

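### The visible criteria for treatment-emergent metabolic syndrome set no baseline condition, so the reported incidence mixes pre-existing with new cases

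*SAP*

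**What the plan says.** SAP 9.2.2 states that "incidence of treatment emergent significant changes in fasting lipids, fasting glucose, and metabolic syndrome will be summarized", by parent study treatment group and overall. The second table of that section is headed "Criteria for Treatment-Emergent Metabolic Syndrome". It has a description column and one column for values at any time after baseline. The five components are absolute thresholds for waist circumference, triglycerides, HDL, supine blood pressure and fasting glucose. The counting rule is "Met 3 Or More of the Above Criteria at a Visit". The footnote identifies baseline as the last measurement before the first open-label dose and says nothing about the subject's status at that point. The general rule in SAP section 9 is that safety analyses use the Safety Sample.

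For rollover subjects, Protocol 3.7.1.1.1 takes the baseline values from the last double-blind visit, including "physical examination, waist circumference, vital signs, ECG, clinical laboratory tests". The SAP reports that no de novo subjects were enrolled. The one exclusion listed under the rollover heading of Protocol Table 3.4.3-1 is "Subjects with a major protocol violation during the course of their participation in the double-blind phase 3 trial".

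**The concern.** A treatment-emergent incidence should count subjects who did not have the condition at the start and acquired it on treatment. As written, the table counts anyone who meets three or more criteria at a post-baseline visit, whatever their status at baseline. Subjects who enter with the syndrome and keep it are counted. Those who enter with it and improve, or who have no evaluable post-baseline visit, are not. The result is neither a prevalence nor an incidence of new onset.

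There is no concurrent control against which pre-existing cases would cancel, so a reader will take the figure as new onset on open-label brexpiprazole. The table is also split by parent treatment group, and baseline is Day 21 of the parent trial. If the prevalence at that day differs between the groups, the difference carries straight into the apparent incidence.

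**Working it through.** **Step 1: does any visible text supply the missing condition?** The documents state no rate for this composite, so there is no figure to reproduce. The check is a comparison of the SAP's own rules for change on treatment.

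| Place in the SAP | How baseline enters |
|---|---|
| 9.2.2, lipid and glucose table | Each row names a baseline category or requires a change of stated size from baseline |
| 9.4, QT/QTc new-onset rows | Absence at baseline is explicit, for example "a subject who attains a value > 500 msec during treatment period but not at baseline" |
| 9.1, treatment-emergent adverse events | An event continuing from baseline counts only if it worsened, was serious or drug-related, or led to death or to a change in or stop of treatment |
| 9.2.2, metabolic syndrome table | No baseline category, no required change, no absence condition |

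The syndrome table is the exception. By the SAP's own usage elsewhere, an unchanged condition carried in from baseline is not treatment-emergent.

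**Step 2: can baseline cases enter?** The single listed rollover exclusion concerns protocol compliance in the parent trial. Nothing listed there removes subjects who already have the syndrome. The parent trials' own eligibility criteria are not in the documents.

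**Step 3: what the rule produces.** Let p be the prevalence at open-label baseline, r the share of those subjects who meet the criteria again after baseline, and i the new-onset rate among subjects free of the syndrome at baseline.

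- Rate as written = p × r + (1 − p) × i
- Rate with a baseline condition and an at-risk denominator = i
- Difference = p × (r − i), which is positive whenever r exceeds i

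The documents give none of p, r or i. All the values below are assumptions, with i = 5%.

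| p | r | Rate as written | Difference from 5% |
|---|---|---|---|
| 10% | 60% | 0.10 × 0.60 + 0.90 × 0.05 = 10.5% | 5.5 points |
| 20% | 80% | 0.20 × 0.80 + 0.80 × 0.05 = 20.0% | 15.0 points |
| 30% | 90% | 0.30 × 0.90 + 0.70 × 0.05 = 30.5% | 25.5 points |

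In the middle row, 100 subjects give 16 persisting and 4 new cases, so 16/20 = 80% of the counted cases were there at baseline. Two effects make up the 15 points. The persisting cases add 16 points to the table. The 4 new cases are 4% of all 100 subjects but 5% of the 80 at risk, and this change of denominator takes 1 point back.

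A wider grid (p from 10% to 40%, r from 60% to 100%, i of 5% or 10%) gives rates as written from 10.5% to 46.0%, with 40% to 93% of counted cases already present at baseline. The two rates agree when p = 0, and otherwise only if r equals i.

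**The case against.** The strongest reply is that the intent is clear. The lead-in sentence and the table title both say treatment-emergent and a baseline footnote is attached, so a careful programmer could exclude baseline cases unprompted. That is possible, but the label is not a rule. The written criteria lead to a different count, and the SAP spells the condition out where it wants it applied.

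Second, SAP 5.2, much of section 10 and the table list in section 12 cannot be read in the public copy, and a convention there could supply the condition. This stands as a limit: the finding covers the visible criteria only.

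Third, most laboratory limits in SAP Appendix 2 are also absolute thresholds without a baseline condition. That is so, but they are presented as values of potential clinical relevance, not as treatment-emergent events.

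Fourth, the size is wholly assumed, and the comparison of 20% with 5% combines the mixing of cases with a change of denominator. Both remarks are correct. The illustration shows direction and mechanism; it does not estimate this trial's result.

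Fifth, this is one descriptive composite with no test attached, and metabolic syndrome is not a named protocol endpoint. The lipid and glucose shifts and the weight and waist changes remain. This limits the harm. Those summaries take one parameter at a time, however, so they cannot recover a composite of three or more criteria met together.

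**Conclusion.** The concern holds for the visible text. The rule in SAP 9.2.2 counts persisting baseline cases as treatment-emergent, and the resulting percentage cannot be read as new onset. The direction is overstatement whenever persistence exceeds the new-onset rate. The amount is unknown, because it depends on a baseline prevalence the documents do not give; the assumed inputs in the three-row table put it between 5.5 and 25.5 percentage points. Possible differences between parent treatment groups rest on the same unknown.

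The primary adverse event analysis, the baseline-conditioned lipid and glucose shifts, and the weight and waist summaries are unaffected. The change should be made, but it does not threaten the trial's main conclusions. Confidence is medium, because parts of the SAP cannot be seen.

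**What to change.** Amend SAP 9.2.2 as follows:

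1. Count a subject as treatment-emergent only if fewer than three criteria are met at open-label baseline and three or more are met at a post-baseline visit.
2. Use as denominator the subjects free of the syndrome at baseline who have evaluable baseline and post-baseline components, and define evaluable.
3. Report baseline prevalence (Day 21 of the parent trial) in a separate row, by parent treatment group and overall.

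A minor clarification can go in at the same time. By Protocol Table 3.7-1, waist is scheduled after baseline only at Week 26 or early termination, and laboratory tests only at Week 12 and at that visit. Four of the five components are thus scheduled at Week 12, all five at Week 26 or early termination, and blood pressure alone at the other five post-baseline visits. The SAP should say whether Week 12 is judged on four components or left out. No figure is claimed for this, and the loss is limited because all five components are scheduled at the final visit.

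The cost is SAP wording and one table program. No new data are needed: baseline waist, vital signs and laboratory values are already collected, and the schedule requires a fasting baseline sample before dosing. The drawback is a smaller denominator, and subjects with incomplete baseline components drop out of this table.

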#### 3.7 Trial Procedures

This is a multicenter, open-label trial designed to assess the safety and tolerability of oral brexpiprazole (OPC-34712) (2-4 mg/day) as treatment in adults with bipolar I disorder. The trial will be conducted on an outpatient basis. The trial comprises a 26-week open-label treatment period with a 21 ( $\pm$  2) day follow-up.

Trial assessment time points are summarized in Table 3.7-1 (open-label treatment phase [Phase B]) and Table 3.7-2 (conversion phase [Phase A]).

34

Table 3.7-1	Schedule	of Assessm	ents - O	pen-label	Treatmen	nt (Phase	B)			
Assessment	Screening	Phase B	Open-Label Treatment Phase Trial Week Visit (± 2 days)				/s)	Follow-up		
	Baseline a (Rollover)	Baseline a (De Novo)	1	2	4	8	12	18	26 / ET b	21 (± 2) days c
ENTRANCE CRITER				_	,					
Informed consent	$\mathbf{X}^{\mathbf{d}}$									
Inclusion/exclusion criteria	X	X								
Medical history	Xe									
CCI		 			I.		1	1	- I	
			_		-					
SAFETY				 	· L			1		I
Physical examination	X f	X g							X	
Waist circumference	X f	X g							X	
Vital signs i	X f	X g	X	X	X	X	X	X	X	
12-lead ECG j	X f	X g					X		X	
Clinical laboratory tests k	X f,l	X g,l					X m		X m	
HbA1c	X f,l	$X^{g,l}$					X m		X m	
Drug screen/blood alcohol n	X f	X g			X		X		X	
Urine pregnancy test (WOCBP only) 	X f	X g	X	X	X	X	X	X	X	
CCI										

Confidential - Proprietary Information

35

Table 3.7-1				P		ıt (Phase ]				
Assessment	Screening	Phase B	Open-Label Treatment Phase Trial Week Visit (± 2 days)						Follow-up	
	/	Baseline a								21 (± 2) days
	Baseline a	(De								
	(Rollover)	Novo)	1	2	4	8	12	18	26/ ET b	
CCI										
Adverse events q	X	X	X	X	X	X	X	X	X	X
Concomitant medications	X	X	X	X	X	X	X	X	X	X
OTHER		•		•			•	•		•
CCI										
										
					•					
Dose adjustment r			X	X	X	X	X	X	X	
Register visit in IWRS	X	X	X	X	X	X	X	X	X	
IMP dispensing	X	X	X	X	X	X	X	X		
IMP accountability			X	X	X	X	X	X	X	

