## 3.7.3.3 Physical Examination and Vital Signs

## 3.7.3.3.1 Physical Examination

A complete physical examination will consist of measurement of height and waist circumference and a review of the following body systems: head, eyes, ears, nose, and throat; thorax; abdomen; urogenital; extremities; neurological; and skin and mucosae. Height will be measured with a stadiometer, measuring stick, or tape. Waist circumference will be measured with each physical examination. The following procedures will aid in the standardization of these measurements:

• The subject should be minimally clothed (ie, lightweight clothing; no heavy overgarments).

- Waist circumference should be recorded before a subject's meal and at approximately the same time at each visit.
- The waist circumference measurement will be accomplished by locating the upper hip bone and the top of the right iliac crest and placing a weighted measuring tape in a horizontal plane around the abdomen at the level of the crest. Before reading the tape measure, the assessor should assure that the tape is snug, but does not compress the skin, and is parallel to the floor. The measurement is to be made at the end of a normal exhalation. 

The principal investigator or his/her appointed designee is primarily responsible to perform the physical examination. If the appointed designee is to perform the physical examination, he/she must be permitted by local regulations and his/her name must be included on the Food and Drug Administration (FDA) Form 1572. Whenever possible, the same individual should perform all physical examinations. Any condition present at the post-treatment physical examination that was not present at the baseline examination should be documented as an AE and followed to a satisfactory conclusion.

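### Metabolic syndrome needs 3 of 5 components at one visit, but waist is not scheduled at Week 12, so that visit is scored on at most 4 components and the any-visit incidence can only be lowered

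*SAP*

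**What the plan says.** SAP 9.2.2 (Criteria for Treatment-Emergent Metabolic Syndrome) lists five components, to be looked for at any time after baseline:

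- central obesity: "Waist Circumference >=102cm(MALE), >=88cm (FEMALE");
- triglycerides of at least 150 mg/dl;
- low HDL: "HDL < 40mg/dl (MALE), <50mg/dl (FEMALE");
- supine blood pressure: "Systolic>=130mmHg and Diastolic>=85mmHg";
- fasting serum glucose of at least 100 mg/dl.

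The syndrome is present when a subject "Met 3 Or More of the Above Criteria at a Visit". The components must therefore coincide at one visit.

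The protocol fixes when each component can be seen. In Table 3.7-1 the row "Waist circumference" is marked at baseline and at Week 26/ET and is blank at Weeks 1, 2, 4, 8, 12 and 18. Section 3.7.3.3.1 ties it to the physical examination ("Waist circumference will be measured with each physical examination"), which has the same schedule. The Week 26/ET list repeats it: "A complete physical examination (including waist circumference) will be performed". The Week 12 list (3.7.1.2.5) has vital signs, ECG and blood samples, but no physical examination and no waist.

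SAP Section 9 sets the default for safety data as observed cases plus the last visit. SAP 3.1 states that no de novo subjects were enrolled, so the waist measurements of the conversion phase play no part.

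**The concern.** Only two scheduled post-baseline visits have the laboratory values the syndrome needs, and at one of them a component is not measured. The visible SAP does not carry a waist value to Week 12, does not set a minimum number of measured components, and does not say whether an incomplete visit counts as negative or as not evaluable. Applied as written to observed data, an unmeasured waist has the same effect as a normal one.

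The any-visit incidence would then combine a five-component visit with a four-component visit. A subject with Week 12 laboratory data and no Week 26/ET visit would be judged on the shorter list alone. In a trial whose stated purpose is safety and tolerability, a metabolic safety summary should not depend on an unstated treatment of a missing component. Two programmers could also obtain different incidences from the same data.

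**Working it through.** The documents state no metabolic syndrome rate, and the sample size is not power-based, so there is no plan figure to reproduce.

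**Step 1. Components available by visit** (Protocol Table 3.7-1 and Sections 3.7.1.2.1 to 3.7.1.2.7)

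| Visit | Waist | Triglycerides, HDL, glucose | Blood pressure | Components |
|---|---|---|---|---|
| Weeks 1, 2, 4, 8, 18 | no | no | yes | 1 |
| Week 12 | no | yes | yes | 4 |
| Week 26/ET | yes | yes | yes | 5 |

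Four is the maximum at Week 12. Fasting is mandatory at Week 26/ET but is asked for only where possible at other visits (Table 3.7-1 footnote), so the fasting glucose component may also be missing at Week 12.

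**Step 2. Patterns lost at Week 12** (no assumptions)

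- Patterns with at least 3 of 5: C(5,3) + C(5,4) + C(5,5) = 10 + 5 + 1 = 16.
- Of these, patterns with at least 3 among the four components other than waist: 2 × [C(4,3) + C(4,4)] = 2 × 5 = 10.
- Lost: waist plus exactly two of the other four, C(4,2) = 6, and 16 − 10 = 6.

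Dropping a component can remove a case but cannot create one, so the direction is certain for this mechanism.

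**Step 3. Rate at the Week 12 visit alone** (prevalences assumed)

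P(≥3 of 5) = P(≥3 of other 4) + P(waist) × P(exactly 2 of other 4), if the components are independent.

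With waist 50%, triglycerides 30%, HDL 35%, blood pressure 15% and glucose 35%: P(≥3 of 4) = 7.0% and P(exactly 2 of 4) = 25.6%. Hence P(≥3 of 5) = 7.0% + 0.50 × 25.6% = 19.8%, and 12.8/19.8 = 65% of that visit's cases are lost. With within-subject correlation 0.4 the rates are 27.4% and 15.0%, a 45% loss. Over three assumed prevalence sets and correlations of 0 to 0.4, the loss at this visit is 43% to 67%.

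With an equal, independent prevalence p for every component:

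| p | 3 of 5 | 3 of 4 |
|---|---|---|
| 0.2 | 5.8% | 2.7% |
| 0.3 | 16.3% | 8.4% |
| 0.4 | 31.7% | 17.9% |

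**Step 4. The any-visit incidence, which is what the SAP reports** (assumptions again)

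A subject is lost only if Week 12 qualifies through waist alone and Week 26/ET either does not qualify or is absent. This was simulated with 300,000 subjects per setting. Base prevalences were waist 45%, triglycerides 30%, HDL 35%, blood pressure 10% and glucose 30%, each scaled by 0.7, 1.0 or 1.3. Correlation between components was 0 or 0.3. Between-visit persistence was 0.5, 0.7 or 0.9, with waist nearly stable at 0.97. Week 26/ET data were present for 100% or 80% of subjects.

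| Setting | Five components at both visits | Waist missing at Week 12 | Relative loss |
|---|---|---|---|
| Central: ×1.0, correlation 0.3, persistence 0.7, all with Week 26/ET | 28.9% | 23.8% | 18% |
| Same, 80% with Week 26/ET | 27.3% | 20.8% | 24% |
| Smallest: ×1.3, correlation 0.3, persistence 0.9, all with Week 26/ET | 40.4% | 35.6% | 12% |
| Largest: ×0.7, correlation 0, persistence 0.5, 80% with Week 26/ET | 9.8% | 6.5% | 34% |

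In the central setting the Week 12 visit alone falls from 21.1% to 9.1%, a 57% loss, against 18% for the any-visit incidence. The difference is what Week 26/ET recovers.

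**The case against.** **A rule may exist out of sight.** The SAP contents page lists 5.2 Handling of Missing Data and a Conventions section (10), but the text of 5.2 and the details of Section 10 are not in the public copy. A carry-forward or incomplete-composite rule could be there. This stands: the schedule mismatch is certain, but the absence of a rule is not, and the sponsor should confirm.

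**The Week 12 loss is not the loss in the result.** A reader might take the 43% to 67% as the under-count of the reported incidence. The documents do not support that. SAP 9.2.2 reports occurrence at any post-baseline visit, Week 26/ET has all five components, and a persistent case is picked up there.

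**Dropouts are mostly covered.** A reader might infer from the planned 175 completers out of about 384 (45.6%) that more than half of subjects are judged on Week 12 alone. They are not, by plan: Table 3.7-1 requires the Week 26 procedures, waist included, at early termination. What remains is subjects with Week 12 laboratory data and no ET visit. Loss to follow-up and consent withdrawal are listed reasons for stopping (Protocol 3.8.3.3), but the documents do not size that group.

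**Net under-reporting is not shown.** The same table sets no condition that the syndrome be absent at baseline, which raises the count, while requiring both systolic and diastolic elevation lowers it. Only this one mechanism is shown to act downward.

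**The components are reported anyway.** Change in waist is summarised (SAP 9.3), and SAP Appendix 2 applies the same cut-offs to fasting triglycerides, HDL and glucose. This limits the harm but does not repair the composite.

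**Carrying waist forward is debatable.** It would let a baseline value help meet a post-baseline criterion and depart from the observed-case default. That is a good reason not to make it the main analysis.

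**Conclusion.** The point holds for this one mechanism. At a scheduled Week 12 visit the stated rule becomes 3 of 4, and 6 of the 16 qualifying patterns cannot be recognised. This follows from the documents alone, as does the downward direction.

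The size does not follow from them. Under the assumed prevalences, correlation, persistence and Week 26/ET attendance above, the any-visit incidence is roughly 12% to 34% lower in relative terms. This is a descriptive secondary safety summary, and the adverse event endpoint is untouched. The conclusion is conditional on no rule in the unpublished parts of the SAP already dealing with it.

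**What to change.** First confirm whether SAP 5.2 or Section 10 already contains a rule. If not, amend SAP 9.2.2:

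1. Make the main metabolic syndrome summary the Week 26/ET (last-visit) incidence among subjects with all five components measured.
2. If the any-visit incidence is kept, score a visit as not met only when the missing components could not bring the total to 3; otherwise call it not evaluable. With waist alone missing, three or four of the other components is met, none or one is not met, and exactly two is not evaluable. State the denominator, including how a subject with one negative and one not-evaluable visit is handled.
3. As a sensitivity summary, score Week 12 with the most recent available waist, labelled as carried forward.

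This is SAP wording and a programming rule on data already collected, with no new procedure. The costs are a smaller evaluable denominator, Week 12-only cases absent from the main summary, and a waist value about 12 weeks old in the sensitivity summary.
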